that are specific to PTSD such as struggles with irritability instead of examples of general stressors. 3) The loving-kindness meditation may not be well-received by all patients. After introducing it, ask participants to try it once then suggest that a previously learned, alternative sitting practices (e.g. body scan) can be used by those who don't like it. 4) I found walking meditation to be very helpful. Introduce this before the 4th session. We expect that modifications will adjust specific aspects to make the training more patient-centered and recovery-oriented, while maintaining the core mindfulness pieces.

**C.2.1 Phase 2 Participants:** For the RCT, 60 eligible patients will be enrolled and randomized to PCBMT or EDU. This sample size was chosen because it will require us to recruit 5 participants per month, which is the

Figure 2. Overview of Study Procedures

To illustrate what type of modifications may result from this feedback, possible input could include: 1) Spend less time in discussion and more time in sitting meditation. 2) When discussing how to apply a skill (e.g., non-reactivity to stress) to real life, use examples

rate of recruitment we believe we will need in a subsequent fully-powered RCT (based on a medium intervention effect size and having 3 years to recruit). We have achieved this rate of recruitment in previous studies with similar samples and methods (see B.1., B.4., B.5.).

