**C.2.2. Phase 2 Recruitment:** Recruitment will use a method used by the PI in several other studies, including the ones detailed in B.3. and B.4. Veterans who screen positive on the annual PC-PTSD screen or have active PTSD symptoms will be referred by their primary care or PC-MHI providers. Referrals will be facilitated with a case-finding procedure: study staff will use medical record data to identify patients that may be eligible for the study based on the annual PTSD screening given to all VHA primary care patients (PC-PTSD). For patients who screen positive, we will ask their primary care providers if a recruitment letter can be sent. All referred Veterans will be sent a letter introducing the study and then will be screened over the phone. In our pilot study, PC-MHI providers were a major source of study referrals. Referral from VHA peer support specialists will also be encouraged. Based on our prior recruitment experience (see B.4., B.5.) we are confident we can recruit 5 participants per month to reach 60 enrolled in one year.

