**C.2.3 Phase 2 Procedures:** The baseline session will include informed consent process (Appendix 2) followed by administration of study measures. Participants will be screened for cognitive impairment with the Blessed Orientation Memory and Concentration measure and suicidality with P4 Screener. The P4 Screener assessed past history, plan, probability, and preventive factors and then classifies respondents as minimal, lower or higher risk for suicide. At the baseline assessment, higher risk participants will be connected to VHA Suicide Prevention Services prior to continuing them in the study. In addition to assessing primary outcomes and patient safety, we plan to test the feasibility of measuring concerns that commonly co-occur with PTSD (depression, insomnia, pain, and alcohol/substance misuse) and potential mediators of the relationship between receiving mindfulness training and changes in PTSD symptoms and psychosocial functioning (mindfulness and emotion regulation skills). Pilot data in this area will help us plan for a future full-scale investigation of potential mediators. Post-treatment assessment will occur upon completion of the assigned intervention. We will re-assess participants at two follow-up points: 16 weeks and 24 weeks post-baseline. This will allow the opportunity to test the feasibility of retaining participants over time so that in the full-scale future trial we can test if any changes observed post-treatment are maintained over time. Given that an aim of this line of research is for PCBMT to serve as a bridge to other more intensive PTSD treatments, within the full-scaled trial, data from the 24 week follow-up will also allow the ability to measure changes associated with any new treatments initiated post study treatment. All research assessments will be administered by research staff blinded to randomization outcome. Participants will be reimbursed \$25 per assessment (\$100 total). Randomization will be stratified based on baseline PCL-5 scores (31-40 vs.  $>40$ ) to equate groups at baseline.

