- *PTSD Checklist-5 (PCL-5)* is a 20-item self-report measure that asks respondents to rate how much they have been bothered by DSM-5 PTSD symptoms in the past month. We will administer this with the extended assessment of traumatic events to ensure that the symptoms reported are related to an event that meets criteria for a traumatic event. Early psychometric study of the PCL-5 indicates excellent reliability and validity. A cut point of 31 along plus meeting Criterion A will be required for study inclusion to allow Veterans with subthreshold PTSD to participate. The total score will be used to indicate PTSD severity at each time point. Since participants must wait to begin the intervention until enough participants are enrolled to form a group, the PCL-5 will be re-administered if participants do not attend class 1 within one month of their baseline interview.
- *Recovery Assessment Scale (RAS)* is a 24-item self-report measure that will assesses various aspects of recovery from the perspective of the Veteran, with an emphasis on hope and self-determination. It covers 5 domains: personal confidence and hope; willingness to ask for help; goal and success orientation; reliance on others; and no domination by symptoms. It has high reliability and good concurrent validity.
- *Patient Health Questionnaire-9 (PHQ-9)* assesses 9 symptoms of depression on a 4-point scale. Participants who endorse the suicidality item will also be administered the P4 screener which assess past history, plan, probability, and preventive factors for suicide.
- *Health Promoting Lifestyle Profile II*

Hypothesized mediators will be assessed with 2 psychometrically sound measures at each time point.

- *Self-Compassion Scale- Short Form*
- *Five Facet Mindfulness Questionnaire (FFMQ)* is a 39-item scale measuring observing, describing, acting with awareness, non-judging, and non-reactivity.
- *Emotion Regulation Questionnaire (ERQ)* is a 10-item self-report measure designed to assess the use cognitive reappraisal and expressive suppression.

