### C.3 Analysis Plan

Aim 1: Gather VHA mental health treatment provider and peer feedback to adapt PCBMT. Co-I [name] will oversee Aim 1 analyses using a Rapid Assessment Process (RAP). This approach is ideal when data needs to be collected and analyzed in one year or less, when only key informants will be interviewed, and when analyses will be deductive. The PI and project coordinator will conduct interviews together with the PI primarily asking questions and the coordinator typing detailed field notes to document responses. A template will be created with a domain name for each interview question (e.g., activating patients, peer roles). The PI, coordinator, and [name] will review the first few sets of field notes collaboratively and summarize content into the domains on the template. After consistency is reached, coders will review the remaining field notes ( $\approx 7$ ) independently. Led by [name], coders will then meet again to analyze summaries and identify suggestions for revisions or aspects seen as helpful that should be maintained within each domain. The PI and Co-Is [name], [name] and [name] will then meet and collectively decide how to modify the protocol. Modifications will only be made if the resulting PCBMT protocol is: 1) feasible to deliver in VHA primary care and 2) stays true to the core mindfulness components. Modifications will be prioritized that are expected to 3) help Veterans develop skills for PTSD symptom management, 4) increase the training’s patient-centeredness, and 5) will affect multiple qualitative domains.

Aim 2: Conduct a pilot RCT (N=60 randomized, n=48 completers) comparing PCBMT to EDU.

**2a.** As this trial will provide us with feasibility information for a larger trial, we will describe the number of participants screened and enrolled per month, proportion of screened participants who are eligible to enroll, completion rates of follow-up assessments, retention rates in study conditions, and the rate and timing of patient drop-out. Recruitment over twelve months will be displayed by plotting the cumulative number of patients enrolled into our study and compared to the anticipated rate of recruitment. Graphs will also be utilized to display rates of intervention and assessment retention at each measurement time. Ninety five percent confidence intervals will be calculated and used in design considerations of a larger trial.

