**2.b.** Participant retention rates in both study interventions will be described with mean, standard deviations and confidence intervals. PCBMT facilitator fidelity will be described quantitatively with the mean number of items endorsed on fidelity checklists. Also items that had lower fidelity will be described to inform future PCBMT training curriculums. Inter-rater reliability will be reported for the 25% of classes rated by an expert observer.

**2.c.** Veteran acceptability (satisfaction, perceived helpfulness, treatment retention): Total CSQ scores and scores on individual CSQ items and Intervention Acceptability items will be described with means, standard deviations and confidence intervals to understand the satisfaction and acceptability in each condition.

**2.d.i.** Patient well-being measured by PTSD severity, depression, health promoting lifestyle behaviors and recovery orientation will be described with means, standard deviations and confidence intervals at each time point by condition. To show central tendency, variation and potential trends over time, means and 95% confidence intervals will be plotted across time for each condition. Additional line plots connecting means across time will overlay the confidence intervals to help illustrate trends. We will also generate an effect size at post-treatment and at each follow-up assessment. Effect sizes will be calculated by dividing the mean difference between conditions by the pooled standard deviation. Then, 95% confidence intervals will be calculated on the effect size by using the non-central t distribution method discussed by Cummings. Graphical methods will be used to plot effects and associated confidence intervals across time which will be used to help design a larger trial. Multi-level modeling will be used to examine group by time effects for each outcome.

**Handling Missing Data.** Multiple Imputation (MI) will be used for missing data. Missing values for variables are predicted using existing values from other variables. These predicted values, called imputes, replace the

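### The analysis plan gives no per-arm count of patients who worsened or became newly suicidal, although the data are collected and patient safety is said to be assessed

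*Combined protocol and SAP*

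**What the plan says.** C.2.3 (Phase 2 Procedures) describes P4 screening at baseline and what follows for higher-risk participants, and then says: "In addition to assessing primary outcomes and patient safety, we plan to test the feasibility of measuring concerns that commonly co-occur with PTSD". C.2.4 (Measures) schedules the functional-status measures, including the PCL-5 and PHQ-9, at baseline, post-treatment, 16 weeks and 24 weeks. Under the PHQ-9 entry it adds: "Participants who endorse the suicidality item will also be administered the P4 screener". So the P4 is given to everyone at baseline and later depends on an item response.

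C.3 (Analysis Plan), item 2.d.i, says that PTSD severity, depression, health behaviours and recovery orientation "will be described with means, standard deviations and confidence intervals at each time point by condition". It adds plots of means, standardised mean differences with intervals, and a multilevel model of group-by-time effects. The rest of C.3 covers qualitative feedback (Aim 1), recruitment, assessment completion, and the rate and timing of drop-out (2a), treatment retention, fidelity and inter-rater reliability (2.b), satisfaction and acceptability (2.c), and multiple imputation.

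The trial size is given as "Conduct a pilot RCT (N=60 randomized, n=48 completers) comparing PCBMT to EDU". The pilot's intervals are meant to inform the next trial: "Ninety five percent confidence intervals will be calculated and used in design considerations of a larger trial".

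**The concern.** An arm can improve on average while some of its patients get worse. Means, standardised differences and group-by-time effects describe the centre of the distribution and do not count patients in the unfavourable tail. No analysis in C.3 uses the P4 class or the PHQ-9 suicidality item on its own, and none sets a threshold for worsening on the PCL-5 or PHQ-9. The acceptability form in C.2.4 is described as asking what improved, and no item on worsening is listed.

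What is at stake is the information handed on. The pilot exists to prepare a full-scale trial. Followed as written, the plan would give that trial no estimate, in either arm, of how often symptoms rise or suicidality newly appears, although the data to calculate one would be on file. C.2.5 says that the comparator classes have not been researched, so the protocol offers no rate for that arm either.

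**Working it through.** **Step 1. The plan's own figure.** C.2.2 says "we are confident we can recruit 5 participants per month to reach 60 enrolled in one year": 5 × 12 = 60, which reproduces. With 48 completers, implied attrition is 1 − 48/60 = 20%. The allocation ratio is not stated. Assuming 1:1, there are 30 randomised and about 24 completers per arm. The documents give no safety figure to reproduce.

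**Step 2. Can the planned tables recover the share who worsen?** They give the mean and SD at each visit, not the distribution of individual change. Under a normal model,

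SD of change = SD × √(2(1 − r)), and share rising by at least t = 1 − Φ((t + mean fall) / SD of change),

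where r is the pre-post correlation. The documents give no PCL-5 SD, mean change, correlation or threshold, so all inputs here are assumptions: mean fall 8, SD 15 at both visits, t = 10.

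| r | SD of change | (10 + 8) / SD of change | Share rising ≥ 10 | Expected number of 24 |
|---|---|---|---|---|
| 0.3 | 17.7 | 1.014 | 15.5% | 3.7 |
| 0.5 | 15.0 | 1.200 | 11.5% | 2.8 |
| 0.8 | 9.5 | 1.897 | 2.9% | 0.7 |

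The visit means and SDs are identical in all three rows. Over mean falls of 5 to 12, SDs of 12 to 15 and r from 0.3 to 0.8, the share runs from 0.2% to 19.9%. At a 5-point threshold it runs from 1.3% to 28.7%, and at 15 points from about 0% to 13.0%. The multilevel model estimates within-patient correlation internally, but only group-by-time effects are planned from it.

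**Step 3. What would a count provide?** Exact (Clopper-Pearson) two-sided 95% intervals; for zero events the upper limit is 1 − 0.025^(1/n).

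| Events | n = 30 | n = 24 |
|---|---|---|
| 0 | 0 to 11.6% | 0 to 14.2% |
| 1 | 0.1 to 17.2% | 0.1 to 21.1% |
| 3 | 2.1 to 26.5% | 2.7 to 32.4% |

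If the true rate were 10%, the chance of seeing at least one case is 1 − 0.9^30 = 95.8%, or 1 − 0.9^24 = 92.0%.

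**Step 4. What would it not provide?** For assumed rates of 5% and 20%, the power of a between-arm comparison (two-sided 0.05 assumed) is 42% by the normal approximation and 24% by Fisher's exact test at 30 per arm, and 35% and 24% at 24 per arm. For 80% power, 76 per arm would be needed.

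**Step 5. Missing patients.** If 0 of 24 worsen among those observed and 6 are missing, the arm's count could be as high as 6 of 30 = 20%. That exceeds the 14.2% upper limit from observed cases, so an observed-case count needs a bound beside it.

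**The case against.** A reader might infer that the protocol promises a safety endpoint and then fails to analyse it. The text does not go that far. The mention of safety is a subordinate clause following the account of P4 screening, and reads naturally as protection of individual participants. Aim 2 lists no safety outcome. The public file also refers to sections B.1 to B.5 and to appendices that it does not contain, so safety reporting elsewhere cannot be excluded. What stands is narrower: C.3 as published has no such summary, and individual follow-up of a suicide screen does not produce a figure by arm.

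A reader might also infer that the pilot is unable to show whether brief mindfulness harms patients and that the added table would settle this. Neither follows. The data are collected, so individual change can still be calculated. A count would not settle causation, given the low power in Step 4. Nor are the shares in Step 2 harm rates. If every patient's true change were a fall of 8 points and all the spread were measurement error or natural fluctuation, the same percentages would cross the threshold. Under some assumptions the share is close to zero.

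Finally, with about 24 to 30 patients per arm the intervals are wide. That is true, but most of this plan is descriptive, and wide intervals are already accepted for its other outcomes.

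**Conclusion.** The point holds as a gap in reporting. Patient safety is named, the relevant data are collected, and C.3 as published has no per-arm count of worsening or new suicidality. Visit means and SDs cannot replace one: under the stated assumptions, the same table fits a share of 2.9% or 15.5% rising by 10 points, and the wider range is 0.2% to 19.9%. This is evidence neither that patients would be harmed nor that harm would be concealed.

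The table would give a usable but imprecise estimate, with an upper limit of 11.6% to 14.2% when no case is seen. These figures rest on 1:1 allocation and 20% attrition; the Step 2 shares rest on assumed PCL-5 inputs and normality. I rate this a cheap improvement and not a flaw in the trial's main purpose.

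**What to change.** Add to 2.d.i one table, by arm and post-baseline visit, giving the number and percentage, with an exact 95% interval, of patients:

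- (a) whose PCL-5 rose from baseline by at least a threshold fixed before any outcome is viewed by arm. Tie the timing to that event because only the assessors are described as blinded. State which PCL-5 is the baseline, since C.2.4 repeats it when class 1 is delayed beyond a month;
- (b) who newly endorsed the PHQ-9 suicidality item, relative to baseline;
- (c) who were newly classed higher risk on the P4, relative to baseline.

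For (b) and (c), use all patients assessed with the PHQ-9 at that visit as the denominator, and also show how many were given the P4, because its later use depends on item endorsement. Report observed cases, not imputed ones, with the numbers assessed and missing, and add a simple bound that counts the missing as worsened. Label the table descriptive, and say that it establishes neither harm nor a between-arm difference and that some score rises will be measurement fluctuation.

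The cost is one extra table and a little analysis time, with no new visits, measures or participants. The downside is wide intervals.

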Primary care patients will be recruited and assessed pre and post intervention and at 16 and 24 week follow-up time points. Each quarter, two months will be spent recruiting and 1 month will be used to conduct the intervention groups. Ideal group size is 6 participants. We anticipate running up three consecutive groups (PCBMT and EDU) at each of the two sites. However, our timeline allows for addition groups as needed. To be eligible, participants must be 1) enrolled in primary care at the Syracuse or Canandaigua VAMC and 2) report significant PTSD symptoms (qualifying criterion A traumatic event plus at least a 31 on the PCL-5). Exclusion criteria are minimized because we seek to include any primary care patients with troubling PTSD symptoms that would normally receive treatment in primary care. Patients will be excluded if they demonstrate symptoms that would not allow them to actively participate in PCBMT: 1) gross cognitive impairment ( $>16$  on the Blessed OMC), 2) suicide attempt or desire to commit suicide in the last month (as measured by P4 screener). To allow the study to isolate the effects of the intervention and ensure patient treatment preferences are honored, patients will be excluded if they 3) have received psychotherapy or change in psychiatric medication outside of VHA primary in the last 2 months, or 4) voice a preference to be directly referred to specialty mental health care. Veterans with depression, anxiety disorders, mild TBI, and alcohol/ substance use disorders will not be excluded, because these problems commonly co-occur with PTSD, and individuals with these conditions have previously benefited from mindfulness training. Patients who receive PC-MHI services will not be excluded, as this is part of the usual primary care services that all Veterans can receive.

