##### Aim 2.a. (recruitment and study retention)

- Number of participants screened per month
- Number enrolled per month
- Proportion of screened participants who are eligible to enroll
- Completion rates of follow-up assessments

Aim 2.b. (participant adherence and retention in treatments, provider and peer treatment fidelity)

- Retention rates in both study interventions
- PCBMT facilitator fidelity. PCBMT facilitators will complete a checklist of essential elements after each class. Co-I's [name] or [name] will observe 25% of all classes and independently rate the fidelity assessment piloted in our earlier PCBMT study (Appendix 3). This assessment was developed based on the guidelines published by Borrelli et al. and documents observations on the delivery and enactment of treatment skills.

Aim 2.c. (intervention acceptability) will be measured at post-treatment by 2 measures.

- The *Client Satisfaction Questionnaire (CSQ)* is an 8-item self-report measure with strong psychometric properties: higher scores are related to treatment completion and symptom reduction.
- *Intervention Acceptability* is a self-report measure created for this study to assess participants' reactions to their assigned intervention, including perceived helpfulness of core intervention components, specific symptoms or functional concerns that improved, and if and how the intervention contributed to meeting the participants' personal recovery goals. Retention (# of sessions attended) will also contribute to measuring intervention acceptability.

Aim 2.d.i. (patient functional status) will be measured at baseline, post-treatment and 16 and 24 week follow-up by 3 measures.

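### The planned effect sizes leave out the baseline scores the trial collects; adjusting for baseline would make them more precise at little cost

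*Combined protocol and SAP*

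**What the plan says.** C.3 Analysis Plan, item 2.d.i, asks for an effect size at post-treatment and at each follow-up: "Effect sizes will be calculated by dividing the mean difference between conditions by the pooled standard deviation". A 95% interval by the non-central t method goes with it. On their use the plan says: "Graphical methods will be used to plot effects and associated confidence intervals across time which will be used to help design a larger trial". The same item adds one sentence on modelling: "Multi-level modeling will be used to examine group by time effects for each outcome". It does not say how that model treats baseline, or that it supplies the plotted effects.

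The baseline scores exist. C.2.4, under Aim 2.d.i, says the outcomes "will be measured at baseline, post-treatment and 16 and 24 week follow-up by 3 measures". C.2.3 uses one of them in the design: "Randomization will be stratified based on baseline PCL-5 scores", cut at 31-40 versus above 40. C.2.4 also allows a second pre-treatment score: "the PCL-5 will be re-administered if participants do not attend class 1 within one month of their baseline interview". The plan does not say which of the two is the baseline.

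Both treatments are given in groups. C.2.1 says: "Ideal group size is 6 participants. We anticipate running up three consecutive groups (PCBMT and EDU) at each of the two sites". It also ties the recruitment rate wanted for the later trial to a calculation "based on a medium intervention effect size and having 3 years to recruit". C.3 expects 48 completers out of 60 randomised.

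**The concern.** At follow-up, part of the spread in a symptom score reflects where each participant started. A raw difference in means carries that spread as noise. A model with the baseline score removes some of it and, under randomisation, estimates the same difference. In a pilot with 48 expected completers the intervals are wide, so precision available without new data is worth having.

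The same model yields r, which decides how much the larger trial would gain from baseline adjustment. As written, the plan reports neither r nor the treatment-group ICC, and both are design inputs for a group-delivered trial.

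Nothing else in the plan clearly covers the point. The multi-level model may use baseline, but it is not tied to the reported effects. Multiple imputation fills in missing values and does not adjust the comparison.

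**Working it through.** **Inputs from the documents.** 60 randomised and 48 completers (C.3), stratification on PCL-5 (C.2.3), ideal group size 6 (C.2.1), raw d with a non-central t interval (2.d.i).

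**Assumed, because the documents do not give them.** 1:1 allocation; r from 0.3 to 0.7; ICC of 0, 0.05 or 0.10 as a share of total outcome variance; 50% or 70% of participants above 40 on PCL-5.

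**The plan's own figures.** 5 per month x 12 months = 60. 48/60 = 0.80, which implies 20% attrition. No power or interval width is stated for the pilot, so there is no precision figure to reproduce.

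**Planned interval at d = 0.5.**
- 24 per arm: -0.078 to 1.072, half-width 0.575.
- 30 per arm (all 60): -0.016 to 1.012, half-width 0.514.

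**Gain by formula, independent participants.** With n = 24 per arm and N = 48, the raw SE in SD units is sqrt(2/24) = 0.289. The adjusted SE is sqrt((1 - r²)(2/n)(1 + 1/(N - 4))):
- r = 0.3: sqrt(0.91 x 0.0833 x 1.0227) = 0.278
- r = 0.5: sqrt(0.75 x 0.0833 x 1.0227) = 0.253
- r = 0.7: sqrt(0.51 x 0.0833 x 1.0227) = 0.208

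These are reductions of about 3.5%, 12% and 28%. At r = 0 the SE rises by about 1%.

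**Gain by simulation.** True d = 0.5, stratified allocation, 24 analysed per arm, 4 to 6 treatment groups per arm, 4,000 to 6,000 trials per cell. Reduction in the SE of the effect size:

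| Setting | r = 0.3 | r = 0.5 | r = 0.7 |
|---|---|---|---|
| ICC 0, outcome unrelated to stratum | 3% | 12% | 26% |
| ICC 0, PCL-5 | 0-2% | 4-7% | 14-18% |
| ICC 0.05, unrelated | 3% | 10% | 19-22% |
| ICC 0.05, PCL-5 | 0-1% | 4-6% | 10-14% |
| ICC 0.10, unrelated | 2-3% | 7-9% | 18-20% |
| ICC 0.10, PCL-5 | about 1% | 3-5% | 8-13% |

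PCL-5 gains less because the stratification already balances part of it. The stratum term adds no precision once baseline PCL-5 is in the model. A repeat with separate code, at ICC 0 and 0.05, agreed to within about two percentage points. The PCL-5 figures do depend on the assumed baseline distribution: a normal distribution truncated at 31, adjusted without a stratum term, gave 0.274 falling to 0.250 at r = 0.5, about 9%.

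**Interval coverage.**
- *Planned interval.* At ICC 0 it covers about 96-98% for PCL-5 at r = 0.5 to 0.7. At ICC 0.05 it covers about 93-96% for PCL-5 and 92-94% for an unrelated outcome.
- *Adjusted interval that assumes independence.* It covers about 90-94% at ICC 0.05 and 84-92% at ICC 0.10, so it is too narrow.
- *Adjusted interval with a treatment-group random effect* (degrees of freedom = number of groups minus 2). It covers about 95-96% at ICC 0.05.

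**Width of the group-aware interval, ICC 0.05.** With baseline, the half-width is 0.67-0.76, 0.62-0.71 and 0.53-0.62 at r = 0.3, 0.5 and 0.7. Without baseline it is 0.69-0.79. Like for like, baseline narrows it by about 3%, 9-10% and 20-23%. Against the planned 0.575 it is wider at r = 0.3 and 0.5, and on either side of it at r = 0.7.

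**Why r matters later.** Take the medium effect as d = 0.5 (an assumption), two-sided 5%, 80% power, before dropout and clustering. The unadjusted need is 64 per arm. With effective effect 0.5/sqrt(1 - r²), that is 0.524, 0.577 and 0.700, it is about 59, 49 and 34 per arm at r = 0.3, 0.5 and 0.7.

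**The case against.** The strongest reply is that nothing is wrong. This is a feasibility pilot sized on recruitment rate, the effect sizes sit among descriptive outputs, and the raw d is a legitimate description. That stands, and it limits the weight of the point.

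A group-by-time model with baseline as one of its time points would already use these scores. That may be so, but the plan specifies neither the model's handling of baseline nor any link to the plotted effects.

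The recommended interval will usually look wider than the planned one. This is true, and at r = 0.7 it can still be wider with few groups. The extra width comes from allowing for clustering, which the planned interval ignores; it is not a cost of using baseline.

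The gain for PCL-5 is small at low r, and the entry cut of 31 may itself lower r. Both stand.

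Finally, r could be computed from the pilot data however d is defined, and it will be imprecise. With 48 completers, an observed r of 0.5 has a 95% interval of about 0.25 to 0.69 (Fisher z), or roughly 60 down to 35 per arm. This is a reason to report r with its uncertainty. The sample sizes above show what r is worth; they are not a loss caused by the planned estimator.

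**Conclusion.** The concern holds as a point of efficiency. The planned effect size is valid but less precise than the collected data allow. Without clustering, the SE reduction from baseline adjustment is about 3% to 26% for outcomes unrelated to the stratum and about 0% to 18% for PCL-5, over r = 0.3 to 0.7. At ICC 0.05 the ranges are about 3-22% and 0-14%. If r were near zero, the SE would be about 1% higher.

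All of this rests on assumed values of r and the ICC, on 1:1 allocation and on 24 analysed per arm. Multiple imputation would give a precision between the 48- and 60-participant cases. The coverage and width figures for the group-aware interval come from one set of simulations and are less firmly established than the SE gains. The change is worth making because it is cheap and the plan intends these effects to inform the next trial. It should rank below any actual error in the plan.

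**What to change.** In item 2.d.i:

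- At each visit, estimate the between-arm difference from a model with arm, that outcome's baseline score and the PCL-5 stratum, or from a longitudinal model with a common baseline mean. The stratum term is there to match the analysis to the randomisation, not for precision.
- For PCL-5, name the pre-randomisation score that defined the stratum as the baseline, so that a re-administered score is not substituted.
- Divide the adjusted difference by the unadjusted pooled SD, so that the result stays comparable with the planned d. Fit the model within each imputed data set before combining.
- Take the interval from a method that allows for estimation of the SD and for treatment groups, for example a group random effect with degrees of freedom based on the number of groups. Do not use an adjusted interval that assumes independence.
- Report r and the ICC with their uncertainty, and keep the raw means and unadjusted d as description.

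The cost is SAP wording, some extra analysis in each imputed data set, a treatment-group identifier and one or two degrees of freedom. The reader should also be told why the interval shown is wider than the planned one unless r is about 0.7.
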